## **Abstract**

Bariatric surgery patients have a variable course of weight loss, maintenance and regain. Few postoperative interventions have been published, with most using traditional behavioral weight loss programs coupled with cognitive behavioral or acceptance and commitment therapy skills. While behavioral weight management principles can be effective in producing weight loss and maintenance, many people are not able to log their intake to track their energy intake on a regular basis, a skill that predicts success. Therefore, other options are needed to optimize weight outcomes in the bariatric population.

Time restricted feeding is one such approach that may help individuals lose weight and improve metabolic health. There are several forms of this approach, but emerging from the pack is promoting an 8-10 hour eating window. This is in comparison to the average adult eating window, typically spanning 12-15 hours from the first eating episode to the last. We propose a pilot trial of a 10 hour time restricted feeding intervention among post-bariatric surgery patients.

We propose group treatment of 10 post-bariatric surgery patients who are interested in losing or stopping gaining weight. They would participate in weekly sessions for 4 weeks, followed by sessions every two weeks for an additional 8 weeks, for a total of 8 sessions/12 weeks. Weights will be monitored at each meeting. Participants will complete an ASA24 food recall weekly to calculate caloric intake and times of eating. They will also complete a daily query of the number of hours they ate within for the previous day.

## **Objectives**

### **Overall objectives**

To test the effects of a 10-hour time restricted eating intervention before and after the 12 weeks of treatment on weight (primary), caloric and macronutritent intake, and a variety of psychosocial measures, including sleep, physical activity, blood pressure and eating behaviors (all secondary).

### **Primary outcome variable(s)**

Aim 1: (Primary Outcome): To compare changes in body weight over 12 weeks in 10 bariatric patients who have undergone bariatric surgery and have completed the pilot study.

Hypothesis: Participants will achieve weight reduction at 12 weeks.

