Participants would be invited to volunteer from our ongoing, longitudinal assessment study of 300 bariatric surgery patients (Psychopathology, Disordered Eating, and Impulsivity as Predictors of Outcomes of Bariatric Surgery, Protocol #823735), 65% of whom come from underserved groups. At Penn Medicine's Metabolic and Bariatric Surgery Program, patients undergo a mental health evaluation and are educated about the dietary and behavioral changes required for success prior to surgery. Postoperatively, they are encouraged to return to the bariatric program for annual follow-up visits, attend support groups, and continue with ongoing care from their primary physicians. Unfortunately, these strategies appear to be insufficient in providing many patients with the dietary and behavioral instruction as well as the social support needed for sustained success. Weight regain threatens the health benefits achieved with bariatric surgery and there is great need for the development of postoperative interventions to promote long term success following bariatric surgery.

Time restricted feeding is emerging as one such approach that may help individuals lose weight and improve metabolic functioning. There are several forms of this approach, but emerging from the pack is promoting an 8-10 hour eating window. This is in comparison to an adult's average eating window, which typically spans 12-15 hours from the first eating episode to the last. We propose a pilot and feasibility trial of a 10 hour time restricted eating intervention among post-bariatric surgery patients. The intervention may be particularly acceptable to individuals from underserved groups who may have limited literacy and numeracy, as well as those with limited access to other health-promoting resources.

We propose group treatment of 10 post-bariatric surgery patients who are interested in losing or stopping gaining weight. They would participate in weekly sessions for 4 weeks, followed by sessions every two weeks for an additional 8 weeks, for a total of 8 sessions. Weights will be

monitored at each meeting. Participants will complete an ASA24 food recall weekly to calculate caloric intake and times of eating. They will complete a daily query to report the number of hours they ate within for the previous day throughout the intervention.

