### **Design**

Non-controlled, single arm intervention study

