### **Study duration**

- Estimated length of time to enroll all subjects and complete the study
- Length of a subject's participation time in study
- Project date of the proposed study

The study should last 6 months. We will recruit participants from an ongoing assessment study. The intervention will last 12 weeks. We will then analyze the data to use in a grant application for October 2019 and a manuscript.

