## **Analysis Plan**

We will use paired t-test analysis to compare the change in weight, blood pressure, calorie and macronutrient intake, and the change in the survey measures before and after the intervention.

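### Aim 1 ties the primary weight comparison to patients who complete the study; if dropout is linked to weight change, the result is biased for all who started

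*Combined protocol and SAP*

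**What the plan says.** Under Primary outcome variable(s), Aim 1 is "To compare changes in body weight over 12 weeks in 10 bariatric patients who have undergone bariatric surgery and have completed the pilot study". The hypothesis directly below it predicts weight loss by week 12 for participants, without mentioning completion. The overall objective likewise asks about the effect on weight over the treatment period with no limit to completers.

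The Abstract gives the number to be treated: "We propose group treatment of 10 post-bariatric surgery patients who are interested in losing or stopping gaining weight". The Background repeats it. The Analysis Plan is a single sentence, beginning "We will use paired t-test analysis to compare the change in weight". It names the test but no analysis population and no handling of a missing 12-week weight. On data collection, the Abstract says "Weights will be monitored at each meeting".

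The design is a "Non-controlled, single arm intervention study". The text between Study duration and Analysis Plan was not available to me, so I cannot say whether the full document has a rule on withdrawal or follow-up.

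**The concern.** The question asked concerns people given the intervention; the comparison as worded concerns people who finish it. These are the same group only under full retention. A paired t-test also needs both weights, so it leaves out anyone not weighed at week 12, even if the completion clause is just loose drafting.

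With no control arm, the before-after change is the entire primary result. No second arm with similar dropout exists to absorb the selection. The result will also be carried forward: "We will then analyze the data to use in a grant application for October 2019 and a manuscript". Finally, the Background describes the study this way: "We propose a pilot and feasibility trial of a 10 hour time restricted eating intervention among post-bariatric surgery patients". In a feasibility trial, how many leave and when is itself a finding, and a completer definition tends to hide it.

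**Working it through.** **Text check.** Ten treated and ten completing are consistent in two cases only: zero dropout, or replacement until ten complete. The available text neither plans nor excludes replacement. The plan gives no derivation of 10 and no SD, dropout rate or alpha, so there is no figure of its own to reproduce. Everything below is illustrative.

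**1. Identity.** With k dropouts among 10 who start:

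completer mean - all-starter mean = (k/10) x (completer mean - dropout mean).

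If dropouts do 1, 2 or 4 kg worse than completers, the loss is overstated by 0.1, 0.2 or 0.4 kg for k = 1; 0.2, 0.4 or 0.8 kg for k = 2; and 0.3, 0.6 or 1.2 kg for k = 3. If dropouts do better, the signs reverse.

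**2. Shift under a dropout model.** Assumptions: n = 10, true mean change 0, SD 3 kg, and the k people with the highest dropout score leave, where that score has correlation rho with weight change (positive rho means poor responders leave). The expected three largest of 10 standard normal values are 1.539, 1.001 and 0.656, so

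shift = -rho x SD x (sum of the k largest)/(10 - k).

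- k = 1: 1.539/9 = 0.171
- k = 2: (1.539 + 1.001)/8 = 0.318
- k = 3: (1.539 + 1.001 + 0.656)/7 = 0.457

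Multiply by 0.3 x 3 = 0.9 or by 0.5 x 3 = 1.5 for the shifts below. The standard error is 3/sqrt(10 - k). The false-loss rates come from 400,000 simulated trials with a two-sided 0.05 paired t-test (alpha assumed), where 2.5% is nominal.

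| Dropouts of 10 | SE (kg) | Shift, rho 0.3 | False loss | Shift, rho 0.5 | False loss |
|---|---|---|---|---|---|
| 1 | 1.00 | -0.15 kg | 3.5% | -0.26 kg | 4.5% |
| 2 | 1.06 | -0.29 kg | 4.4% | -0.48 kg | 6.5% |
| 3 | 1.13 | -0.41 kg | 5.2% | -0.68 kg | 8.3% |

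Repeat runs differ by about 0.01 kg and 0.1 percentage point. The shifts are 0.15 to 0.36 of a standard error at rho 0.3 and 0.26 to 0.60 at rho 0.5; these ratios do not depend on the SD. By the identity in step 1, rho 0.3 means that dropouts do about 0.154/0.1 = 1.5 kg (k = 1) to 0.411/0.3 = 1.4 kg (k = 3) worse than completers.

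**3. Other directions.** At rho 0 the shift is zero and the false-loss rate is 2.5%. At rho -0.3 (good responders leave) the shift is +0.15 to +0.41 kg, which understates loss. In the extreme case where exactly the worst 1, 2 or 3 leave, the false-loss rate is 8.7%, 18.6% or 30.6%. For k = 3 the shift is then 0.457 x 3 = 1.37 kg, above one standard error; nothing in the documents points to that case.

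**4. Effect of weighing dropouts.** Weighing all 10 at week 12 gives no shift and 2.5%. Weighing one of two dropouts leaves -0.13 kg (3.3%) at rho 0.3 and -0.21 kg (3.9%) at rho 0.5. Weighing two of three leaves -0.11 kg (3.1%) and -0.18 kg (3.5%). These partial figures assume that those weighed are a random subset of the dropouts, which is favourable.

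**5. Carrying the last weight forward.** This simulation used a true loss of 3.0 kg, linear courses, SD 3 kg and weighing noise of 0.8 kg. The chance of leaving per session was 6% if not losing and 1% if losing, or 9% and 1.5%. When leaving depends on observed weight, completers give -3.24 and -3.36 kg and the last recorded weight gives -2.76 and -2.65 kg: errors of about the same size in opposite directions. When leaving depends on the true slope, completers give -3.23 and -3.33 kg and the last weight -2.92 and -2.88 kg. Weighing everyone gives -3.00 kg.

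**The case against.** The completion clause may be one loosely drafted phrase that takes full retention for granted. The objective, the hypothesis, Aim 2 and the Analysis Plan carry no such limit. That is fair, and a reader should not infer that a completer population was chosen on purpose. The clause is still the only statement of who enters the primary comparison, and it disagrees with the objective.

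A reader might also infer that the two tens contradict each other, that the reported loss will be too large, or that the plan makes no provision for dropouts. The documents support none of these. Replacement would reconcile the numbers. The direction depends on who leaves. A follow-up rule may stand in text I could not see, although Aim 1 would then still need to match it.

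The completer mean is also unbiased for completers; the bias exists only relative to all who started. That stands, and the point is limited accordingly.

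On size, the objection is strong. Every numerical input is assumed. Coverage of the nominal 95% interval falls only to 94.6% to 93.7% at correlation 0.3, and to 94.0% to 90.9% at 0.5. With SD 3 kg and correlation 0.3, the interval's half-width is about 2.2 to 2.6 kg. Sampling error therefore exceeds this bias in all the moderate scenarios. The answer is that the interval shows sampling error but does not show selection, and readers can judge selection only if the number who started and their outcomes are reported.

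**Conclusion.** The point holds as a mismatch between the population in Aim 1 and the one in the objective and hypothesis. Its consequence is conditional: if dropout is related to weight change, the completer mean misstates the effect in all who started, in a direction that cannot be known in advance. With no dropout or unrelated dropout there is no bias, though unrelated dropout still costs precision.

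The likely size is modest: about 0.15 to 0.68 kg, with false significant loss of 3.5% to 8.3% against 2.5%. This rests on an assumed SD of 3 kg, 1 to 3 dropouts, correlation 0.3 to 0.5 and a two-sided 0.05 test. The shift stays below one standard error across that range. This is an inexpensive improvement to a small pilot and does not invalidate the design.

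**What to change.** In Aim 1, drop the completion condition, define the population as all participants who start treatment and have a baseline weight, and give 10 as the number enrolled. If replacement is intended, say so.

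In the Analysis Plan, state that:

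- A 12-week weight will be sought from everyone, including those who stop attending.
- The primary paired comparison, with a 95% CI, uses everyone with a baseline and a 12-week weight, whether or not they completed the sessions. A paired comparison cannot include someone with no 12-week weight, so this should be explicit.
- If any 12-week weight is still missing, a sensitivity analysis in all who started will use the session weights already collected. A mixed model over sessions is one option, with the last or baseline weight carried forward as a further check. Carrying forward can understate a real loss.
- The completer-only result is secondary and is reported with the number and timing of dropouts.

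The cost is one sentence in Aim 1, a few in the Analysis Plan, and some effort to weigh people who stop attending. Recruitment may ease that: "Participants would be invited to volunteer from our ongoing, longitudinal assessment study of 300 bariatric surgery patients". The documents do not say when that study weighs its participants. The reported change may be less favourable if poor responders are the ones who leave.

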### **Secondary outcome variable(s)**

Aim 2: (Secondary Outcomes): To compare changes before and after the 12-week intervention in caloric and macronutrient intake, eating behavior, sleep behavior, physical activity, psychosocial outcomes, and metabolic disease risk factors.

Hypothesis: Participants will report lower caloric intake, more favorable changes in macronutrient intake and eating behavior, more positive changes in sleep quality, participate in more physical activity, and experience more favorable improvements in relevant psychosocial variables at treatment end as compared to baseline.

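### Do the several untargeted t-tests in Aim 2, some with no stated favorable direction, need a hierarchy or multiplicity adjustment?

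*Combined protocol and SAP*

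**What the plan says.** The Objectives section makes weight the primary outcome and marks all other outcomes as secondary. Under Secondary outcome variable(s), Aim 2 lists seven domains: "caloric and macronutrient intake, eating behavior, sleep behavior, physical activity, psychosocial outcomes, and metabolic disease risk factors".

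The hypothesis that follows covers six of the seven. It opens: "Participants will report lower caloric intake, more favorable changes in macronutrient intake and eating behavior, more positive changes in sleep quality". It adds that participants will "participate in more physical activity" and "experience more favorable improvements in relevant psychosocial variables at treatment end as compared to baseline". Only caloric intake and physical activity have an explicit direction; the other four are to change for the better, with no sign given. Metabolic risk factors appear in the aim but not in the hypothesis.

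The Analysis Plan is one sentence. It begins "We will use paired t-test analysis to compare the change in weight, blood pressure, calorie and macronutrient intake" and goes on to the survey measures. It gives no significance level, sidedness, number of tests, order among the secondary outcomes or adjustment, and it does not use the word exploratory.

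The Design section describes a single arm without a control. The Background calls the study a pilot and feasibility trial of 10 patients. Study duration says the data will go into a grant application and a manuscript.

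**The concern.** Several predictions are each tested separately, and nothing limits the overall chance of a false positive. A reader of the manuscript could meet one nominally significant improvement among many outcomes and not know whether it was predicted or picked out afterwards.

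The macronutrient wording adds to this. A questionnaire score usually has a built-in good end; protein, fat and carbohydrate intake do not. With no sign stated, a rise or a fall could be presented as support. The phrase about relevant psychosocial variables also leaves room to choose. With 10 participants and no control group, a chance result in the grant application would be hard to tell from a real one. One could therefore ask for a single key secondary outcome, a Holm adjustment, or an exploratory label with directions spelled out.

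**Working it through.** The plan states no error rate, so there is no figure of its own to reproduce. The question is how large the risk is, and what the proposed changes would do about it.

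**Inputs**
- Sample size 10, one arm, paired t-test (Background; Design; Analysis Plan).
- Seven secondary domains (Aim 2). The number of individual variables is not stated. Assumed range: k = 7 (one test per domain), 10 (for example three macronutrients and two blood-pressure values) and 15 (several scales per questionnaire).
- Alpha is not stated. Assumed: 0.05 per test.

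**Chance of a false improvement on one test, with no true change**
- Two-sided 0.05 with the favorable direction fixed: a = 0.05/2 = 0.025. The other half of the errors are apparent worsenings.
- One-sided 0.05, or direction left open so that either sign could be claimed: a = 0.05.

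**Chance of at least one, independent outcomes: 1 − (1 − a)^k**

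| k | a = 0.025 | a = 0.05 |
|---|---|---|
| 7 | 1 − 0.975^7 = 16.2% | 1 − 0.95^7 = 30.2% |
| 10 | 1 − 0.975^10 = 22.4% | 1 − 0.95^10 = 40.1% |
| 15 | 1 − 0.975^15 = 31.6% | 1 − 0.95^15 = 53.7% |

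If, among ten tests, only three macronutrients have an open direction: 1 − 0.975^7 × 0.95^3 = 1 − 0.8376 × 0.8574 = 28.2%.

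The probability passes one half only from k = 14 at a = 0.05, or k = 28 at a = 0.025.

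**Correlation.** Calories and macronutrients come from the same food recalls, so independence is pessimistic. Simulated paired t-tests (n = 10, 40,000 runs, equal correlation 0.5, signs oriented so that positive is favorable) gave:
- k = 7: 11.9% with direction fixed, 24.0% with either sign counted.
- k = 10: 15.2% and 30.2%.

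**What the remedies would do**
- *Mean change with an unadjusted 95% confidence interval in place of a p-value.* The interval excludes zero exactly when the two-sided paired t-test gives p < 0.05. The error rate is the same.
- *Formal adjustment.* At two-sided 0.05, n = 10 gives 80% power for a mean change of 0.996 standard deviations of the change. For ten tests, the Bonferroni level (also Holm's first step) is 0.05/10 = 0.005. The critical t on 9 degrees of freedom rises from 2.262 to 3.690, so the observed change needed for significance rises from 2.262/√10 = 0.715 to 3.690/√10 = 1.167 standard deviations. Power for a true change of 0.996 falls from 80% to about 37% (noncentral t, 9 degrees of freedom).
- *Calories as the key secondary.* Nothing in the documents ranks calories above the other secondary outcomes, so this would be a preference.

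**The case for a change.** The strongest case for a change is that secondary does not mean exploratory. Aim 2 states a hypothesis, the results are meant for a manuscript and a grant application, and a few sentences would let readers separate a predicted result from a selected one at almost no cost. The risk exceeds 5% in every scenario above.

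Most of this stands as description. The macronutrient direction is missing, and so are alpha and sidedness. What does not stand is the claim that a chance improvement is likely. The 40% and 54% figures for 10 and 15 tests count a significant result in either direction, so they describe a false improvement only if tests are one-sided at 0.05 or every outcome's sign is open. Calories and physical activity have stated directions, and questionnaire scores generally carry their own. Metabolic risk factors should not be counted among the hypotheses at all.

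Nor can missing questionnaire detail be charged to the plan: a section before the Analysis Plan was not part of the text reviewed and may describe the measures.

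**Conclusion.** The observation is accurate, but no change to the plan is called for. Under 0.05 per test, no true change and independence, the chance of at least one false improvement is about 16% to 30% for seven tests and 22% to 40% for ten, and less with positive correlation. The upper ends require one-sided testing or an open direction for every outcome. The number of tests and alpha are assumptions.

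The primary comparison on weight is untouched. Declaring the other outcomes secondary already ranks them below it, and the uncontrolled pilot design of 10 patients limits what any of them can show. Naming a direction for each macronutrient and calling the results exploratory would put in writing what an analyst reporting such a pilot would sensibly do, without altering the tests or their error rate. Adjustment or a single key secondary outcome would reduce false positives at a substantial loss of power, and reasonable statisticians differ on whether that is worthwhile in a study meant to generate ideas for a larger one.

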## **Background**

Bariatric surgery is an increasingly utilized treatment for persons with a body mass index (BMI) 40 kg/m^2 or 35 kg/m^2 in the presence of obesity-related comorbidities. Early results tend to be good, with most patients losing 20-35% of their weight in the first 6-24 months after surgery and experiencing improvements in obesity-related comorbidities. These outcomes, however, are not universal and vary between patients and across surgical procedures. It is estimated that 20-30% of patients experience significant weight regain within the first few postoperative years. Individuals from minority groups appear to be at increased risk for these outcomes. Among individuals who underwent Roux-en-Y gastric bypass (GB), for example, non-Hispanic black and Hispanic patients experienced smaller weight losses than their non-Hispanic white counterparts. Reasons for these suboptimal outcomes are not fully understood, but likely involve both physiological processes and behavioral factors (e.g., failure to make sustained dietary and physical activity changes necessary for weight maintenance). Evidence suggests that preoperative psychosocial status and functioning can contribute to suboptimal weight losses and/or postoperative psychosocial distress. Much of the work in this area has focused on formal psychopathology with particular emphasis on mood disorders as well as binge eating disorder (BED). Individuals who present for bariatric surgery also have high lifetime rates of substance use disorders. Some studies have suggested that the presence of preoperative psychopathology is associated with suboptimal weight losses and less positive psychosocial outcomes.

Participants would be invited to volunteer from our ongoing, longitudinal assessment study of 300 bariatric surgery patients (Psychopathology, Disordered Eating, and Impulsivity as Predictors of Outcomes of Bariatric Surgery, Protocol #823735), 65% of whom come from underserved groups. At Penn Medicine's Metabolic and Bariatric Surgery Program, patients undergo a mental health evaluation and are educated about the dietary and behavioral changes required for success prior to surgery. Postoperatively, they are encouraged to return to the bariatric program for annual follow-up visits, attend support groups, and continue with ongoing care from their primary physicians. Unfortunately, these strategies appear to be insufficient in providing many patients with the dietary and behavioral instruction as well as the social support needed for sustained success. Weight regain threatens the health benefits achieved with bariatric surgery and there is great need for the development of postoperative interventions to promote long term success following bariatric surgery.

Time restricted feeding is emerging as one such approach that may help individuals lose weight and improve metabolic functioning. There are several forms of this approach, but emerging from the pack is promoting an 8-10 hour eating window. This is in comparison to an adult's average eating window, which typically spans 12-15 hours from the first eating episode to the last. We propose a pilot and feasibility trial of a 10 hour time restricted eating intervention among post-bariatric surgery patients. The intervention may be particularly acceptable to individuals from underserved groups who may have limited literacy and numeracy, as well as those with limited access to other health-promoting resources.

We propose group treatment of 10 post-bariatric surgery patients who are interested in losing or stopping gaining weight. They would participate in weekly sessions for 4 weeks, followed by sessions every two weeks for an additional 8 weeks, for a total of 8 sessions. Weights will be

monitored at each meeting. Participants will complete an ASA24 food recall weekly to calculate caloric intake and times of eating. They will complete a daily query to report the number of hours they ate within for the previous day throughout the intervention.

